#### 6.2. Exclusion Criteria

Patients will be excluded from study enrollment if they meet any of the following criteria at screening and/or enrollment:

- [9] are investigative site personnel directly affiliated with this study and their immediate families. Immediate family is defined as a spouse, biological or legal guardian, child, or sibling.
- [10] are Lilly or Covance employees.
- [11] are currently enrolled in a clinical study involving an investigational product or any other type of medical research judged not to be scientifically or medically compatible with this study.
- [12] have known allergies to lasmiditan, related compounds, or any components of the formulation of lasmiditan.
- [13] are persons who have previously received the investigational product in this study, withdrawn from this study or any other study investigating lasmiditan.
- [14] have participated, within the last 30 days, in a clinical study involving an investigational product. If the previous investigational product has a long half-life, 5 half-lives or 30 days (whichever is longer) should have passed.
- [15] have an abnormal blood pressure, defined as systolic blood pressure ≤90 or >155 mmHg or diastolic blood pressure ≤50 or >95 mmHg (applies at screening only). Up to 2 additional measurements may be undertaken after an appropriate resting interval at screening to confirm eligibility.

- [16] have clinically significant ECG findings, including a QT interval corrected for heart rate using Fridericia's formula (QTcF) value >450 ms (males) or >470 ms (females), clinically significant bradycardia, cardiac block, or bradyarrhythmias.
- [17] have a history of, show evidence of, or are undergoing treatment for significant active neuropsychiatric disease (for example, manic depressive illness, schizophrenia, major depressive disorder).
- [18] have an increased risk of seizures based on a history of:
  - one or more seizures;
  - head trauma with loss of consciousness or a post-concussive syndrome or lifetime history of head trauma with persistent neurological deficit (focal or diffuse) within the past 6 months;
  - central nervous system infection or transient ischemic attack (TIA); stroke with persistent neurological deficit (focal or diffuse). TIA is defined as "mini-stroke" caused by temporary disturbance of blood supply to an area of the brain, which results in a sudden, brief decrease in brain function;
  - brain surgery;
  - electroencephalogram (EEG) with paroxysmal (epileptiform) activity (isolated spikes waves, repetitive bursts of sharp waves, paroxysmal activity, frank seizures, spike-wave complexes, or sharp-slow wave complexes, or as locally defined);
  - brain structural lesion, including developmental abnormalities, as determined by examination or imaging studies (except hydrocephalus treated by shunt and without neurological deficit).
- [19] have a history of gastrointestinal surgery, or a history of or current irritable bowel syndrome, mal-absorptive disorders, or other gastrointestinal motility disorders. Appendectomy, splenectomy, and cholecystectomy are considered as acceptable.
- [20] have current hypertension, unless adequately controlled by a medication that is permitted per the study protocol, in the opinion of the investigator.
- [21] have significant history of, or currently have, any other cardiovascular, respiratory (including bronchospasm or bronchial asthma, or chronic obstructive airways disease), hepatic, renal, gastrointestinal, endocrine, hematological, or neurological disorders capable of significantly altering the absorption, metabolism, or elimination of drugs; of constituting a risk when taking the investigational product; or of interfering with the interpretation of data, in the opinion of the investigator.
- [22] show evidence of substance use disorder as defined in Diagnostic and Statistical Manual of Mental Disorders (DSM) 5, or have positive findings on the drugs of abuse test at the screening visit.

- [23] show evidence of human immunodeficiency virus (HIV) infection and/or positive human HIV antibodies.
- [24] show evidence of hepatitis C and/or positive hepatitis C antibody.
- [25] show evidence of hepatitis B and/or positive hepatitis B surface antigen.
- [26] are women with a positive pregnancy test or who are lactating.
- [27] have used or intend to use any migraine prevention treatments (including, but not limited to, propranolol or topiramate) within 30 days prior to dosing and until the follow-up visit.
- [28] have donated blood of more than 500 mL within the 3 months prior to the screening visit.
- [29] have an average weekly alcohol intake that exceeds 21 units per week (males up to age 65) and 14 units per week (females and males over 65), or are unwilling to follow the study site's alcohol consumption restrictions while resident (1 unit = 12 oz or 360 mL of beer; 5 oz or 150 mL of wine; 1.5 oz or 45 mL of distilled spirits).
- [30] in the opinion of the investigator or sponsor, are unsuitable for inclusion in the study.
- [31] have a recent history of a suicide attempt (30 days within screening visit and any time between screening visit and baseline); or are clinically judged by the investigator to be at risk for suicide.

# 6.2.1. Rationale for Exclusion of Certain Study Candidates

Criteria [1] through [8] define a population with episodic migraine that is suitable for evaluation in a Phase 1 study. Criteria [9] and [10] prevent conflict of interest in study participants. Criteria [11] through [31] exclude medical conditions, medication intolerance, and concomitant medication use that may confound the assessment of study endpoints.

## 6.3. Lifestyle and/or Dietary Requirements

Throughout the study, patients may undergo medical assessments and review of compliance with requirements before continuing in the study.

## 6.3.1. Meals and Dietary Restrictions

Lasmiditan should be administered after a 4-hour fast, as far as is reasonably practicable, and food should not be consumed until 4 hours postdose. The actual timing of meals on dosing days will be captured in the electronic case report form (eCRF). Water may be consumed ad libitum at all times.

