#### Rationale:

Lasmiditan is a small molecule 5-HT1F receptor agonist being developed for the acute treatment of migraine. Acute migraine attacks are frequently accompanied by some gastrointestinal symptoms, such as nausea and vomiting. Gastric motility studies also indicated that many migraine patients developed gastroparesis during acute migraine attacks. Changes in gastric motility may lead to changes in pharmacokinetics (PK) of drugs for migraine abortive treatment, which may reduce the effectiveness of migraine treatment. The goal of this study is to assess the PK of lasmiditan in migraineurs during acute migraine attacks and during inter-ictal periods.

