# 2. Schedule of Activities

**Study Schedule Protocol H8H-MC-LAHC** 

	Screening	Periods 1 and 2				Follow-up/ED (4-7 days after last dose)	Comments
Procedure	≤28 days prior to Day 1, Period 1	Day 1	Day 2	Day 3	Day 4		
Informed Consent	X						
Patient Admission to Study Site		X					Period 1 admission at onset of migraine symptoms.
Patient Discharge from Study Site			X				Discharge on Day 2 after last assessment, at investigator discretion.
Investigational Product Administration		X, indicates time = 0					Period 1 dose to be administered within 24 h of onset of migraine symptoms; Period 2 dose to be administered at approximately the same time of day as the Period 1 dose, following a washout of at least 1 week.
Medical History	X						
Medication Review	X	X	X	X	X	X	
Height	X						
Weight	X					X	
Adverse Event Recording		X	X	X	X	X	
Vital Signs (supine)	X	Predose, 1, 2, 4, and 8 h	24 h	48 h	72 h	X	Supine triplicate BP and pulse rate, except screening. Predose vital signs can be taken any time prior to dosing on Day 1. Time points may be added if warranted and agreed upon between Lilly and the investigator. Sampling windows: 1-2 h ±5 min; 4 h ±10 min; 8 h ±20 min; 24-72 h ±30 min.
Orthostatic Vital Signs	X	Predose, 1, 2, 4, and 8 h	24 h			X	Single orthostatic BP/pulse rate. Last triplicate vital sign can be used as the supine vital sign for calculation of orthostatic changes. Time points may be added if warranted and agreed upon between Lilly and the investigator.

	Screening	Periods 1 and 2				Follow-up/ED (4-7 days after last dose)	Comments
Procedure	≤28 days prior to Day 1, Period 1	Day 1	Day 2	Day 3	Day 4		
Clinical Lab Tests	X	Predose	X			X	See Appendix 2, Clinical Laboratory Tests, for details.
Pregnancy Test	X	Predose				X	Serum pregnancy test will be performed at screening. Urine pregnancy test will be performed at every admission period prior to dose and at follow-up/ED, if applicable.
Physical Exam /Medical Assessment	X	Predose	X		X	X	Full physical exam at screening; symptom- driven medical assessment at all other times as deemed necessary by the investigator.
12-Lead ECG	X	Predose	24 h			X	Single ECGs to be collected at each time point.
C-SSRS and Self-Harm Supplement	X	X	X			X	At screening 'Baseline' questionnaire to be used, all other timepoints use 'Since Last Visit' questionnaire.

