# 5. Study Design

## 5.1. Overall Design

Study H8H-MC-LAHC is a multi-center, open-label study with 2 study periods to be conducted in patients with episodic migraine. Patients will receive 1 oral dose of lasmiditan during an acute migraine attack (Period 1), and 1 oral dose of lasmiditan during their inter-ictal period (Period 2). There will be a washout period of at least 1 week between doses.

All patients will participate in a screening visit. Eligible patients will be instructed to telephone the study site when they feel the onset of migraine symptoms, to arrange to attend for an immediate inpatient stay. Each patient must be admitted to the study site with continuing migraine symptoms within 28 days of the screening visit. Provided they are still experiencing migraine symptoms, patients will receive a single dose of 200 mg lasmiditan on arrival at the study site; this will be defined as Period 1, Day 1. The first dose of lasmiditan must be administered within 24 hours of onset of migraine symptoms; the time of administration will be defined as time = 0. Patients may be discharged from the study site after the last scheduled Day 2 assessment has been performed (24 hours postdose), at the discretion of the investigator, with subsequent Period 1 assessments performed on an outpatient basis. Patients will then telephone the study site again at the onset of their next migraine attack to arrange for a second inpatient stay, which should be scheduled for as soon as possible after the expected resolution of the migraine attack (ie, the next day or, if the migraine is expected to continue into the next day, the following day). This second visit should occur at least 1 week, and up to 4 weeks (but may be extended beyond 4 weeks if necessary, at the investigator's discretion) after their first lasmiditan dose, and will be defined as Period 2, Day 1. Provided the patient is still in their inter-ictal period (defined as not currently experiencing migraine symptoms) on arrival at the site, they will be readmitted as an inpatient and receive a single dose of 200 mg lasmiditan. Patients may be discharged from the study site after the last scheduled Day 2 assessment is complete, at the discretion of the investigator with subsequent Period 2 assessments performed on an outpatient basis. All patients will return for a follow-up visit 4 to 7 days after their last dose of lasmiditan

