# 7.2. Method of Treatment Assignment

All patients will receive the same treatments in the same sequence and will not be subject to randomization.

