## 7.2.1. Selection and Timing of Doses

The dose administered during a migraine attack must be administered within 24 hours of the onset of migraine symptoms. For each patient, the doses will be administered at approximately the same times on each day, although the dosing times will vary between patients. The actual time of all dose administrations will be recorded in the patient's eCRF.

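### Should the SAP pre-specify a by-period check of fasting status, given that the migraine dose is unscheduled and the inter-ictal dose is arranged?

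*Protocol*

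**What the plan says.** Both periods share one fasting rule (Protocol Section 6.3.1): "Lasmiditan should be administered after a 4-hour fast, as far as is reasonably practicable", and "food should not be consumed until 4 hours postdose". Meal times on dosing days are recorded in the eCRF.

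The two doses come about differently (Protocol Section 5.1). In Period 1 the patient calls at symptom onset, is admitted at once and is dosed on arrival. The Period 2 visit is arranged after a later attack, "which should be scheduled for as soon as possible after the expected resolution of the migraine attack". The order is fixed (Protocol Section 7.2): "All patients will receive the same treatments in the same sequence and will not be subject to randomization". Clock time is matched within patient. The Schedule of Activities has "Period 2 dose to be administered at approximately the same time of day as the Period 1 dose", and Protocol Section 7.2.1 has "For each patient, the doses will be administered at approximately the same times on each day".

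SAP Section 9.3.2 models log Cmax and log AUC with period and patient only, and tests tmax with a Wilcoxon signed rank test. SAP Section 9.1 lists everything in the database but summarises only what the SAP details, and the SAP text does not mention meals or fasting. SAP Section 8 weighs protocol deviations when populations are assigned. Protocol Section 10.3 and SAP Sections 3 and 9.3.2 leave room for additional analyses. SAP Section 3 places the detailed outputs in a separate TFL shell document, which was not available for this review.

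**The concern.** Because the order is fixed, anything that differs systematically between an attack visit and an arranged visit becomes part of the period contrast. Fed state is a natural candidate. A patient called in at short notice may have eaten recently, whereas a patient coming to a planned visit can skip a meal. The opposite is also plausible, since the protocol's rationale notes that "Acute migraine attacks are frequently accompanied by some gastrointestinal symptoms, such as nausea and vomiting", and a nauseated patient may not eat.

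SAP Section 9.3.2 reads the PK contrast as evidence about gastric motility. On the protocol's own figures, a 1 h food delay is 40% to 100% of the usual tmax of 1 to 2.5 h (1/2.5 and 1/1). A net excess of fed doses in one period could therefore imitate delayed emptying on tmax, or hide it. On Cmax and AUC, an excess in the migraine period could offset a true fall. The information needed to judge this is collected, yet no by-period summary or sensitivity analysis is fixed in advance.

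**Working it through.** **Inputs from the documents.** n = 12 completers and CV 40% (Protocol Section 10.1). Food effect about +1 h on median tmax and about ×1.20 on Cmax and AUC, and usual tmax about 1 to 2.5 h (Protocol Section 3.2). Samples every 0.5 h from 0.5 to 4 h (Schedule of Activities).

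**Assumptions.** The net share p of patients fed in Period 1 only is not in the documents; it is taken as 10%, 25% and 50%. Of 12 patients, 25% is 3 and 50% is 6. The high-fat effect serves as an upper bound, with half of it as an alternative.

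**The plan's own figure.** SD = √ln(1 + 0.40²) = 0.385. Half-width = exp(1.645 × 0.385/√12) − 1 = exp(0.1829) − 1 = 20.07%, the stated 20.1%. This uses 0.385 as the SD of the within-patient log-ratio. If the 40% describes each period and the periods are uncorrelated, the SD is 0.385 × √2 = 0.545.

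**Cmax and AUC.** The geometric mean ratio is multiplied by 1.20^p:

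| p | Ratio shift, ×1.20 | Ratio shift, ×1.10 | 90% CI coverage, ×1.20, SD 0.385 | Same, SD 0.545 |
|---|---|---|---|---|
| 10% | +1.8% | +1.0% | 89.7% | 89.7% |
| 25% | +4.7% | +2.4% | 87.5% | 88.8% |
| 50% | +9.5% | +4.9% | 80.8% | 85.0% |

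With the ×1.10 effect, coverage stays at or above 87.4% throughout. If the excess lies in Period 2, the ×1.20 shifts are −1.8%, −4.5% and −8.7%.

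**tmax.** The mean difference moves by p × 1 h: 0.10, 0.25 and 0.50 h, against a 0.5 h sampling grid. The table gives the share of simulated trials with signed-rank p<0.10 when migraine has no effect (12 pairs, exact test, zeros dropped, 20,000 trials per cell). Fasted tmax is assumed uniform on the 0.5 h grid over the stated spread. Half shared means that half the patients have the same fasted tmax in both periods.

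| Spread, delay, pairing | p = 0 | 10% | 25% | 50% |
|---|---|---|---|---|
| 1–2.5 h, 1 h, independent | 7.6% | 9.9% | 18.9% | 48.3% |
| 1–2.5 h, 1 h, half shared | 3.0% | 6.9% | 22.0% | 62.5% |
| 1–2.5 h, 0.5 h, independent | 7.5% | 8.1% | 11.2% | 21.2% |
| 1–2.5 h, 0.5 h, half shared | 3.0% | 4.7% | 11.3% | 31.0% |
| 0.5–4 h, 1 h, independent | 9.1% | 9.7% | 12.5% | 22.2% |
| 0.5–4 h, 1 h, half shared | 4.9% | 6.6% | 14.6% | 35.9% |
| 0.5–4 h, 0.5 h, independent | 9.1% | 9.1% | 9.8% | 12.4% |
| 0.5–4 h, 0.5 h, half shared | 4.5% | 6.5% | 9.6% | 20.5% |

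At 10% imbalance the rate stays below the nominal 10% in every setting. At 25% it runs from about 10% to 22%. The figures of 48% and above need a net imbalance of 6 of 12 patients, the full high-fat effect and a narrow tmax spread, all together. The 1 to 2.5 h range covers peak times across doses of 25 to 400 mg and is not stated to be the individual range at 200 mg, so the wider spread is a reasonable alternative.

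**What a restricted analysis would give.** Half-width on m pairs = exp(t(0.95, m−1) × SD/√m) − 1. At SD 0.385 it is 22.1% (m = 12), 27.0% (9) and 37.3% (6). At SD 0.545 it is 32.6%, 40.2% and 56.5%. The bias it would look for on Cmax and AUC is about 2% to 10%.

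**The case for a change.** The best case for a change is that it is cheap and touches the interpretation of a primary endpoint. The data are already collected. Matching clock time does not fix the time since the last meal, and the postdose food rule controls only one side. Under a best-effort rule a short fast need not count as a deviation, so the deviation review may not catch it. SAP Section 9.1 confines summaries to what the SAP details. In a small open-label study, a check named beforehand carries more weight than one chosen after the tmax result is known.

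The factual part stands: the gap is in the SAP text, tmax is the most exposed endpoint, and pre-specification has some value. The step to a needed change does not. A by-period table of time since last meal would restate a listing of 24 to 40 dosing occasions (12 to 20 patients, two periods), which any analyst puzzled by tmax can read.

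An analysis restricted to pairs with the same fasting status is a debatable trade. Cutting at 4 h treats fasts of 4.5 h and 14 h as alike but 3.9 h and 4.1 h as different. It ignores meal content, which is not described as recorded. It also conditions on eating, which the attack itself may change. With 6 to 9 pairs its interval is far wider than the bias in question. Neither addition would alter a primary result, and the documents attach no decision rule to tmax.

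**Conclusion.** No change to the plan follows. Fed state could differ between the periods in either direction, or not at all. The shared fasting rule, the matched time of day and the postdose food restriction all limit the difference. For Cmax and AUC the effect is at most about 5% at a net imbalance of 3 in 12 and under 10% at 6 in 12, taking the high-fat effect as the ceiling. For tmax, a 25% imbalance raises the chance of p<0.10 to about 10% to 22%, from 3% to 9% with none; only a large imbalance does real harm.

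These sizes rest on assumed imbalances, an assumed delay of 0.5 to 1 h, assumed tmax spreads and assumed within-patient correlation. The TFL shells could not be checked and may already contain such a summary. What remains is missing detail that the recorded meal times, the listing rule and the provision for additional analyses let the study team fill. Anyone interpreting a tmax difference should look at the meal listing first.

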# 6.3.2. Caffeine, Alcohol, and Tobacco

**Caffeine** – Patients will abide by study site restrictions for consumption of xanthine- or caffeine-containing food and drinks while resident.

**Alcohol** – Patients will abide by study site alcohol consumption restrictions while resident.

**Tobacco** – Patients will refrain from smoking from 1 hour prior to dosing until 4 hours postdose, and will abide by any study site smoking restrictions while resident.

#### 6.4. Screen Failures

Individuals who do not meet the criteria for participation in this study (screen failure) may be re-screened once. The interval between re-screenings should be at least 1 week. Each time re-screening is performed, the individual must sign a new informed consent form (ICF) and will be assigned a new identification number.

#### 7. Treatment

#### 7.1. Treatment Administered

Lasmiditan will be supplied as film-coated tablets each containing 100 mg or 200 mg of lasmiditan as free base.

One 200-mg tablet or two 100-mg tablets of lasmiditan will be administered orally with approximately 240 mL of room temperature water on each dosing day, in a sitting position. In the event of migraine symptoms, patients may be permitted to receive lasmiditan in a semi-recumbent position, at the discretion of the investigator. Patients will not be allowed to lie supine for 2 hours after dosing, unless clinically indicated or for study procedures.

The investigator or designee is responsible for:

- explaining the correct use of the investigational product to the site personnel;
- verifying that instructions are followed properly;
- maintaining accurate records of investigational product dispensing and collection;
- and returning all unused medication to Lilly or its designee at the end of the study.

#### 7.1.1. Packaging and Labeling

Each tablet of lasmiditan contains 100 mg or 200 mg of active ingredient and is provided as bulk supplies in bottles.

The investigational product will be labeled according to the country's regulatory requirements.

# 7.2. Method of Treatment Assignment

All patients will receive the same treatments in the same sequence and will not be subject to randomization.

## 7.2.1. Selection and Timing of Doses

The dose administered during a migraine attack must be administered within 24 hours of the onset of migraine symptoms. For each patient, the doses will be administered at approximately the same times on each day, although the dosing times will vary between patients. The actual time of all dose administrations will be recorded in the patient's eCRF.

# 7.3. Blinding

This is an open-label study.

#### 7.4. Dose Modification

Dose modification will not be allowed during the study. Should a patient fail to tolerate the first dose of lasmiditan, they may be withdrawn from the study at the discretion of the investigator.

#### 7.5. Preparation/Handling/Storage/Accountability

The investigator or designee must confirm all investigational product was received in good condition, and any discrepancies are reported and resolved before use of the study treatment.

Only participants enrolled in the study may receive investigational product or study materials, and only authorized site staff may supply or administer investigational product. All investigational product should be stored in an environmentally controlled and monitored (manual or automated) area in accordance with the labeled storage conditions with access limited to the investigator and authorized site staff.

The investigator, institution, or the head of the medical institution (where applicable) is responsible for study treatment accountability, reconciliation, and record maintenance (such as receipt, reconciliation, and final disposition records).

